10.3.2. Visit 2 (Day 15 ± 1 day)

This visit will be performed for safety purposes. The following assessments will be performed at Visit 2 (Day 15):

- Vital signs: blood pressure and heart rate
- 12-lead ECG
- Review study drug accountability and compliance
- Suicidality assessment using the C-SSRS
- Record concomitant therapy
- Record AEs/SAEs

10.3.3. Visit 3 (Month 3/Week 13) \pm 5 days)

The following assessments will be performed at Visit 3 (Month 3):

- Blood/urine sampling for the following laboratory tests:
 - Hematology: RBC count, total and differential WBC count (basophils, eosinophils, lymphocytes, monocytes, and neutrophils), platelet count, hemoglobin, hematocrit, MCV, MCH, and MCHC
Note: All total WBC and differential WBC counts will be blinded during the study.
 - Blood chemistry: sodium, potassium, chloride, calcium, magnesium, phosphate, blood urea nitrogen, random glucose, albumin, alkaline phosphatase, creatinine, SGPT/ALT, SGOT/AST, GGT, amylase, total bilirubin, conjugated bilirubin, hemoglobin A1c. Abnormal laboratory parameters inconsistent with clinical presentation of MS or suspicious of underlying medical condition should be repeated for accuracy. If an increase of amylase above the clinically notable value (≥ 300 U/L) is observed at any post randomization visit, lipase should be tested to determine the origin of elevated amylase (pancreatic versus extra pancreatic)
 - Urinalysis: leukocytes, specific gravity, bilirubin, blood, glucose, ketones, pH, protein, and urobilinogen.
 - Urine beta-hCG (females of childbearing potential only). If the urine pregnancy test is positive, do not dose and confirm with a serum pregnancy test.
- Vital signs: blood pressure and heart rate
- Dispense study drug and patient diary
- Review study drug accountability and compliance
- EDSS and neurological assessment
- Pulmonary function tests including FEV₁ and FVC measurements
- Suicidality assessment using the C-SSRS
- Record concomitant therapy
- Record AEs/SAEs

10.3.4. Visit 4 (Month 6/Week 26 \pm 5 days)

The following assessments will be performed at Visit 4 (Month 6):

- Blood/urine sampling for the following laboratory tests:
 - Hematology: RBC count, total and differential WBC count (basophils, eosinophils, lymphocytes, monocytes, and neutrophils), platelet count, hemoglobin, hematocrit, MCV, MCH, and MCHC
Note: All total WBC and differential WBC counts will be blinded during the study.

- Blood chemistry: sodium, potassium, chloride, calcium, magnesium, phosphate, blood urea nitrogen, random glucose, albumin, alkaline phosphatase, creatinine, SGPT/ALT, SGOT/AST, GGT, amylase, total bilirubin, conjugated bilirubin, hemoglobin A1c, and total cholesterol, triglycerides, HDL and LDL. Abnormal laboratory parameters inconsistent with clinical presentation of MS or suspicious of underlying medical condition should be repeated for accuracy. If an increase of amylase above the clinically notable value (≥ 300 U/L) is observed at any post randomization visit, lipase should be tested to determine the origin of elevated amylase (pancreatic versus extra pancreatic)
 - Urinalysis: leukocytes, specific gravity, bilirubin, blood, glucose, ketones, pH, protein, and urobilinogen
 - Urine beta-hCG (females of childbearing potential only). If the urine pregnancy test is positive, do not dose and confirm with a serum pregnancy test.
 -
 - Standard PK sampling: PK samples are to be taken 2 to 6 hours following administration
- Vital signs: blood pressure and heart rate
 - Dispense study drug and patient diary
 - Review study drug accountability and compliance
 - EDSS and neurological examination
 - MSFC AND LCLA
 - MSQOL-54
 - Pulmonary function tests including FEV₁ and FVC measurements
 - OCT evaluation
 - Suicidality assessment using the C-SSRS
 - Record concomitant therapy
 - Record AEs/SAEs

10.3.5. Visit 5 (Month 9/Week 39 \pm 5 days)

The following assessments will be performed at Visit 5 (Month 9):

- Blood/urine sampling for the following laboratory tests:
 - Hematology: RBC count, total and differential WBC count (basophils, eosinophils, lymphocytes, monocytes, and neutrophils), platelet count, hemoglobin, hematocrit, MCV, MCH, and MCHCNote: All total WBC and differential WBC counts will be blinded during the study.

- Blood chemistry: sodium, potassium, chloride, calcium, magnesium, phosphate, blood urea nitrogen, random glucose, albumin, alkaline phosphatase, creatinine, SGPT/ALT, SGOT/AST, GGT, amylase, total bilirubin, conjugated bilirubin, hemoglobin A1c. Abnormal laboratory parameters inconsistent with clinical presentation of MS or suspicious of underlying medical condition should be repeated for accuracy. If an increase of amylase above the clinically notable value (≥ 300 U/L) is observed at any post randomization visit, lipase should be tested to determine the origin of elevated amylase (pancreatic versus extra pancreatic)
- Urinalysis: leukocytes, specific gravity, bilirubin, blood, glucose, ketones, pH, protein, and urobilinogen.
- Urine beta-hCG (females of childbearing potential only). If the urine pregnancy test is positive, do not dose and confirm with a serum pregnancy test.
- Vital signs: blood pressure and heart rate
- Dispense study drug and patient diary
- Review study drug accountability and compliance
- EDSS and neurological examination
- Suicidality assessment using the C-SSRS
- Record concomitant therapy
- Record AEs/SAEs

10.3.6. Visit 6 (Month 12/Week 52 \pm 5 days)

Note: Subjects are to be instructed not to take their dose of study drug at home, and will be administered study drug at the clinic after laboratory procedures have been completed. Subjects should arrive at the clinic in a fasted state.

The following assessments will be performed at Visit 6 (Month 12):

- Blood/urine sampling for the following laboratory tests (to be performed predose):
 - Hematology: RBC count, total and differential WBC count (basophils, eosinophils, lymphocytes, monocytes, and neutrophils), platelet count, hemoglobin, hematocrit, MCV, MCH, and MCHC
Note: All total WBC and differential WBC counts will be blinded during the study.
 - Blood chemistry: sodium, potassium, chloride, calcium, magnesium, phosphate, blood urea nitrogen, random glucose, albumin, alkaline phosphatase, creatinine, SGPT/ALT, SGOT/AST, GGT, amylase, total bilirubin, conjugated bilirubin, hemoglobin A1c, and total cholesterol, triglycerides, HDL and LDL. Abnormal laboratory parameters inconsistent with clinical presentation of MS or suspicious of underlying medical condition should be repeated for accuracy. If an increase of amylase above the clinically notable value (≥ 300 U/L) is observed at any post

- randomization visit, lipase should be tested to determine the origin of elevated amylase (pancreatic versus extra pancreatic)
- Urinalysis: leukocytes, specific gravity, bilirubin, blood, glucose, ketones, pH, protein, and urobilinogen
 - Urine beta-hCG (females of childbearing potential only). If the urine pregnancy test is positive, do not dose and confirm with a serum pregnancy test.
 - Coagulation panel: PT and PTT
 - sTSH
 - [REDACTED]
 - [REDACTED]
 - Standard PK sampling: PK sample is to be taken prior to dose administration
- Administer study drug
 - Complete physical examination: including evaluation of heart, lung, head and neck, abdominal, neurological, skin, and extremities
 - Weight
 - Vital signs: blood pressure and heart rate
 - 12-lead ECG
 - Dispense study drug and patient diary
 - Review study drug accountability and compliance
 - Brain MRI
 - EDSS and neurological examination
 - MSFC AND LCLA
 - MSQOL-54
 - Pulmonary function tests including FEV₁ and FVC measurements, and DLCO
 - OCT evaluation
 - Dermatological examination
 - Suicidality assessment using the C-SSRS
 - Record concomitant therapy
 - Record AEs/SAEs

10.3.7. Visit 7 (Month 15/Week 65 ± 5 days)

The following assessments will be performed at Visit 7 (Month 15):

- Blood/urine sampling for the following laboratory tests:

CONFIDENTIAL

The information contained herein may not be used, disclosed, or published without the written consent of Receptos.

- Hematology: RBC count, total and differential WBC count (basophils, eosinophils, lymphocytes, monocytes, and neutrophils), platelet count, hemoglobin, hematocrit, MCV, MCH, and MCHC
Note: All total WBC and differential WBC counts will be blinded during the study.
- Blood chemistry: sodium, potassium, chloride, calcium, magnesium, phosphate, blood urea nitrogen, random glucose, albumin, alkaline phosphatase, creatinine, SGPT/ALT, SGOT/AST, GGT, amylase, total bilirubin, conjugated bilirubin, hemoglobin A1c. Abnormal laboratory parameters inconsistent with clinical presentation of MS or suspicious of underlying medical condition should be repeated for accuracy. If an increase of amylase above the clinically notable value (≥ 300 U/L) is observed at any post randomization visit, lipase should be tested to determine the origin of elevated amylase (pancreatic versus extra pancreatic)
- Urinalysis: leukocytes, specific gravity, bilirubin, blood, glucose, ketones, pH, protein, and urobilinogen
- Urine beta-hCG (females of childbearing potential only). If the urine pregnancy test is positive, do not dose and confirm with a serum pregnancy test.
- Vital signs: blood pressure and heart rate
- Dispense study drug and patient diary
- Review study drug accountability and compliance
- EDSS and neurological examination
- Suicidality assessment using the C-SSRS
- Record concomitant therapy
- Record AEs/SAEs

10.3.8. Visit 8 (Month 18/Week 78 \pm 5 days)

The following assessments will be performed at Visit 8 (Month 18):

- Blood/urine sampling for the following laboratory tests:
 - Hematology: RBC count, total and differential WBC count (basophils, eosinophils, lymphocytes, monocytes, and neutrophils), platelet count, hemoglobin, hematocrit, MCV, MCH, and MCHC
Note: All total WBC and differential WBC counts will be blinded during the study.
 - Blood chemistry: sodium, potassium, chloride, calcium, magnesium, phosphate, blood urea nitrogen, random glucose, albumin, alkaline phosphatase, creatinine, SGPT/ALT, SGOT/AST, GGT, amylase, total bilirubin, conjugated bilirubin, hemoglobin A1c, and total cholesterol, triglycerides, HDL and LDL. Abnormal laboratory parameters inconsistent with clinical presentation of MS or suspicious of underlying medical condition should be repeated for accuracy. If an increase of

amylase above the clinically notable value (≥ 300 U/L) is observed at any post randomization visit, lipase should be tested to determine the origin of elevated amylase (pancreatic versus extra pancreatic)

- Urinalysis: leukocytes, specific gravity, bilirubin, blood, glucose, ketones, pH, protein, and urobilinogen
- Urine beta-hCG (females of childbearing potential only). If the urine pregnancy test is positive, do not dose and confirm with a serum pregnancy test.
- [REDACTED]
- Vital signs: blood pressure and heart rate
- Dispense study drug and patient diary
- Review study drug accountability and compliance
- EDSS and neurological examination
- MSFC AND LCLA
- MSQOL-54
- Suicidality assessment using the C-SSRS
- Record concomitant therapy
- Record AEs/SAEs

10.3.9. Visit 9 (Month 21/Week 91 \pm 5 days)

The following assessments will be performed at Visit 9 (Month 21):

- Blood/urine sampling for the following laboratory tests:
 - Hematology: RBC count, total and differential WBC count (basophils, eosinophils, lymphocytes, monocytes, and neutrophils), platelet count, hemoglobin, hematocrit, MCV, MCH, and MCHC
Note: All total WBC and differential WBC counts will be blinded during the study.
 - Blood chemistry: sodium, potassium, chloride, calcium, magnesium, phosphate, blood urea nitrogen, random glucose, albumin, alkaline phosphatase, creatinine, SGPT/ALT, SGOT/AST, GGT, amylase, total bilirubin, conjugated bilirubin, hemoglobin A1c. Abnormal laboratory parameters inconsistent with clinical presentation of MS or suspicious of underlying medical condition should be repeated for accuracy. If an increase of amylase above the clinically notable value (≥ 300 U/L) is observed at any post randomization visit, lipase should be tested to determine the origin of elevated amylase (pancreatic versus extra pancreatic)
 - Urinalysis: leukocytes, specific gravity, bilirubin, blood, glucose, ketones, pH, protein, and urobilinogen

- Urine beta-hCG (females of childbearing potential only). If the urine pregnancy test is positive, do not dose and confirm with a serum pregnancy test.
- Vital signs: blood pressure and heart rate
- Dispense study drug and patient diary
- Review study drug accountability and compliance
- EDSS and neurological examination
- Suicidality assessment using the C-SSRS
- Record concomitant therapy
- Record AEs/SAEs

10.3.10. Visit 10 (Month 24/Week 104 ± 5 days)

Patients are expected to remain in Part B for 24 months.

The following assessments will be performed at Visit 10 (Month 24):

- Blood/urine sampling for the following laboratory tests:
 - Hematology: RBC count, total and differential WBC count (basophils, eosinophils, lymphocytes, monocytes, and neutrophils), platelet count, hemoglobin, hematocrit, MCV, MCH, and MCHC
Note: All total WBC and differential WBC counts will be blinded during the study.
 - Blood chemistry: sodium, potassium, chloride, calcium, magnesium, phosphate, blood urea nitrogen, random glucose, albumin, alkaline phosphatase, creatinine, SGPT/ALT, SGOT/AST, GGT, amylase, total bilirubin, conjugated bilirubin, hemoglobin A1c, and total cholesterol, triglycerides, HDL and LDL. Abnormal laboratory parameters inconsistent with clinical presentation of MS or suspicious of underlying medical condition should be repeated for accuracy. If an increase of amylase above the clinically notable value (≥ 300 U/L) is observed at any post randomization visit, lipase should be tested to determine the origin of elevated amylase (pancreatic versus extra pancreatic)
 - Urinalysis: leukocytes, specific gravity, bilirubin, blood, glucose, ketones, pH, protein, and urobilinogen
 - Urine beta-hCG (females of childbearing potential only). If the urine pregnancy test is positive, do not dose and confirm with a serum pregnancy test.
 - Coagulation panel: PT and PTT
 - sTSH
 - [REDACTED]
 - [REDACTED]

- Standard PK sampling: PK samples are to be taken 2 to 6 hours following administration
- Complete physical examination: including evaluation of heart, lung, head and neck, abdominal, neurological, skin, and extremities
- Weight
- Vital signs: body temperature, blood pressure and heart rate
- 12-lead ECG
- If patients will continue on treatment, dispense study drug and patient diary
- Review study drug accountability and compliance
- Brain MRI
- EDSS and neurological examination
- MSFC AND LCLA
- MSQOL-54
- Pulmonary function tests including FEV₁ and FVC measurements, and DLCO
- OCT evaluation
- Dermatological examination
- Suicidality assessment using the C-SSRS
- Record concomitant therapy
- Record AEs/SAEs

10.4. Unscheduled Relapse Assessment Visit (Part A and Part B)

Patients should be evaluated by following the onset of any new or recurrent neurological symptoms as detailed in [Section 9.1.2.3](#).

During an unscheduled relapse assessment visit the following assessments will be performed:

- Blood/urine sampling for the following laboratory tests:
 - Hematology: RBC count, total and differential WBC count (basophils, eosinophils, lymphocytes, monocytes, and neutrophils), platelet count, hemoglobin, hematocrit, MCV, MCH, and MCHC
Note: All total WBC and differential WBC counts will be blinded during the study.
 - Blood chemistry: sodium, potassium, chloride, calcium, magnesium, phosphate, blood urea nitrogen, random glucose, albumin, alkaline phosphatase, creatinine, SGPT/ALT, SGOT/AST, GGT, amylase, total bilirubin, conjugated bilirubin, hemoglobin A1c

- Urinalysis: leukocytes, specific gravity, bilirubin, blood, glucose, ketones, pH, protein, and urobilinogen
- Vital signs: body temperature, blood pressure and heart rate
- EDSS and neurological examination
- MSFC and LCLA
- Suicidality assessment using the C-SSRS
- Record concomitant therapy
- Record AEs/SAEs

After the Unscheduled Relapse Assessment Visit, patients should return to their usual visit schedule.

10.5. Early Termination Visit

Patients who prematurely discontinue study treatment will be asked to complete an early termination visit. The following assessments will be performed:

- Blood/urine sampling for the following laboratory tests:
 - Hematology: RBC count, total and differential WBC count (basophils, eosinophils, lymphocytes, monocytes, and neutrophils), platelet count, hemoglobin, hematocrit, MCV, MCH, and MCHC
Note: All total WBC and differential WBC counts will be blinded during the study.
 - Blood chemistry: sodium, potassium, chloride, calcium, magnesium, phosphate, blood urea nitrogen, random glucose, albumin, alkaline phosphatase, creatinine, SGPT/ALT, SGOT/AST, GGT, amylase, total bilirubin, conjugated bilirubin, hemoglobin A1c. Abnormal laboratory parameters inconsistent with clinical presentation of MS or suspicious of underlying medical condition should be repeated for accuracy. If an increase of amylase above the clinically notable value (≥ 300 U/L) is observed at any post randomization visit, lipase should be tested to determine the origin of elevated amylase (pancreatic versus extra pancreatic)
 - Urinalysis: leukocytes, specific gravity, bilirubin, blood, glucose, ketones, pH, protein, and urobilinogen
 - Urine beta-hCG (females of childbearing potential only). If the urine pregnancy test is positive, do not dose and confirm with a serum pregnancy test.
 - Coagulation panel: PT and partial thromboplastin time PTT
 - sTSH
 - [REDACTED]
 - [REDACTED]

- PK sampling
- Complete physical examination: including evaluation of heart, lung, head and neck, abdominal, neurological, skin, and extremities
- Weight
- Vital signs: body temperature, blood pressure and heart rate
- 12-lead ECG
- Review study drug accountability and compliance
- Brain MRI
- EDSS and neurological examination
- MSFC and LCLA
- MSQOL-54
- Pulmonary function tests including FEV₁, FVC, and DLCO measurements
- OCT evaluation
- Dermatological examination
- Suicidality assessment using the C-SSRS
- Record concomitant therapy
- Record AEs/SAEs

10.6. Follow-Up

Patients will be asked to return for a follow-up visits 4 weeks after their last dose of study treatment of either Part A or Part B.

During the follow-up visit the following assessments will be performed:

- Blood/urine sampling for the following laboratory tests:
 - Hematology: RBC count, total and differential WBC count (basophils, eosinophils, lymphocytes, monocytes, and neutrophils), platelet count, hemoglobin, hematocrit, MCV, MCH, and MCHC
Note: All total WBC and differential WBC counts will be blinded during the study.
 - Blood chemistry: sodium, potassium, chloride, calcium, magnesium, phosphate, blood urea nitrogen, random glucose, albumin, alkaline phosphatase, creatinine, SGPT/ALT, SGOT/AST, GGT, amylase, total bilirubin, conjugated bilirubin, hemoglobin A1c. Abnormal laboratory parameters inconsistent with clinical presentation of MS or suspicious of underlying medical condition should be repeated for accuracy. If an increase of amylase above the clinically notable value (≥ 300 U/L) is observed at any post randomization visit, lipase should be tested to determine the origin of elevated amylase (pancreatic versus extra pancreatic)

- Urine beta-hCG (females of childbearing potential only). If the urine pregnancy test is positive, do not dose and confirm with a serum pregnancy test.
- Vital signs: body temperature, blood pressure and heart rate
- 12-lead ECG
- Suicidality assessment using the C-SSRS
- Record previously ongoing AEs/SAEs

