- 16 PK samples on Day 1 and Week 12 will be taken predose. PK samples at Week 4 and Week 24 will be taken 2 to 6 hours following study drug administration; patients should record the time of study drug administration for these visits. An additional PK sample will be obtained for patients with any AE resulting in unblinding, discontinuation, or SAE.

CONFIDENTIAL

The information contained herein may not be used, disclosed, or published without the written consent of Receptos.

Table 2 Schedule of Assessments – Part A: Optional Blinded Extension, Early Termination, and Follow-up Visits

Procedure	Blinded Extension ¹			Un-scheduled Relapse Visit ⁴	Early Term ⁵	Follow Up Visit 4 weeks after last dose (±5d)
	Day 183 (W26) ² (±1d)	Every 12 weeks ³ (±5d)	End of Study ³			
Clinical laboratory tests ⁶		X	X	X	X	X
Urine/serum pregnancy (women of childbearing potential only) ⁷		X	X		X	X
Coagulation panel			X		X	
Total Ig (IgA, IgG, IgM)						
Complete physical examination			X		X	
Weight			X		X	
Vital Signs	X	X	X	X	X	X
12-lead ECG	X	X	X		X	X
Study drug administration	X	X	X			
Administer study drug at clinic						
Dispense study drug and patient diary		X				
Study drug accountability and compliance check	X	X	X		X	
Brain MRI		X ⁸	X ⁸		X	
EDSS and neurological examination		X	X	X	X	
MSFC and LCLA		X	X	X	X	
MSQOL-54			X		X	
Pulmonary function tests ⁹		X	X		X	
OCT ¹⁰			X		X	
Dermatological (skin) examination			X			
C-SSRS	X	X	X	X	X	X
Standard PK sampling ¹¹					X	
Plasma biomarkers						
Prior/Concomitant therapy	X	X	X	X	X	X
AEs/SAEs	X	X	X	X	X	X

ECG = electrocardiogram, MRI = magnetic resonance imaging, EDSS = Expanded Disability Status Scale, MSFC = Multiple Sclerosis Functional Composite, LCLA = low-contrast letter acuity test; MSQOL = Multiple sclerosis quality of life, OCT = optical coherence tomography, C-SSRS = Columbia- Suicide Severity Rating Scale, PK = pharmacokinetics, AE/SAE = adverse events/serious AE

CONFIDENTIAL

The information contained herein may not be used, disclosed, or published without the written consent of Receptos.

Footnotes to Table 2

- 1 The blinded extension is optional.
- 2 A visit for safety assessments will be performed 14 days after the first dose of study medication.

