- 12 Pulmonary function tests will include FEV₁ and FVC measurements at all the above indicated visits. In addition, DLCO will be assessed at screening, Month 12, and Month 24. If any abnormalities occur, they will be followed until such time as resolution is confirmed or no further improvement is expected by the investigator (based on a follow-up period of not less than 3 months).
- 13 If abnormal OCT findings, or visual signs or symptoms of macular edema are observed, a general ophthalmologic examination including eye history, visual acuity, and dilated ophthalmoscopy will also be performed.
- 14 PK sample on Day 1 and Month 12 will be taken predose. PK samples at Month 6 (Visit 4) and Month 24 (Visit 10) will be taken 2 to 6 hours following study drug administration; patients should record the time of study drug administration for these visits. An additional PK sample will be obtained for patients with any AE resulting in unblinding, discontinuation, or SAE.
15. Body temperature is recorded at screening, EOT or early term visits only.

Table 4 Schedule of Assessments – Part B: Unscheduled Relapse, Early Termination, and Follow-up Visits

Procedure	Unscheduled Relapse Visit¹	Early Termination²	Follow Up Visit 4 weeks after last dose
Clinical laboratory tests ³	X	X	X
Urine/serum pregnancy test (females of childbearing potential only) ⁴		X	X
Coagulation panel		X	
Total Ig (IgA, IgG, IgM)			
Complete physical examination		X	
Weight		X	
Vital signs	X	X	X
12-lead ECG		X	X
Study drug accountability and compliance check		X	
Brain MRI ⁵		X	
EDSS and neurological examination	X	X	
MSFC and LCLA	X	X	
MSQOL-54		X	
Pulmonary Function Tests ⁶		X	
OCT ⁷		X	
Dermatological (skin) examination		X	
C-SSRS	X	X	X
Standard PK sampling		X	
Plasma biomarkers			
Prior/Concomitant therapy	X	X	
AEs/SAEs	X	X	X

ECG = electrocardiogram, MRI = magnetic resonance imaging, EDSS = Expanded Disability Status Scale, MSFC = Multiple Sclerosis Functional Composite, LCLA = low-contrast letter acuity test; MSQOL = Multiple sclerosis quality of life, OCT = optical coherence tomography, C-SSRS = Columbia- Suicide Severity Rating Scale, PK = pharmacokinetics, AE/SAE = adverse events/serious AE

Footnotes to Table 4

- 1 The Unscheduled Relapse Assessment Visit will be conducted in the case of a suspected relapse (see [Section 9.1.2.3](#)). After the Unscheduled Relapse Assessment Visit, patients should return to their usual visit schedule.

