12.1. Adverse Events (AEs)

The AE definitions and reporting procedures provided in this protocol comply with current CFR 21 Part 312. An AE is any untoward medical occurrence that does not necessarily have a causal relationship with the investigational medicinal product. An AE can therefore be any unfavorable or unintended sign, including an abnormal laboratory finding, symptom or disease temporally associated with the use of an investigational medicinal product whether or not considered related to the investigational medicinal product.

Relapses and MS disease progression will be monitored as study endpoints, but will not be recorded as AEs.

AEs will be monitored throughout the entire study. Investigators will ask the patient at each visit if they have experienced any untoward occurrence since the last study visit. All AEs will be recorded on the eCRFs provided: a description of the event, severity, time of occurrence, duration, any action (e.g. treatment and follow up tests) and the outcome should be provided along with the Investigator's assessment of the relationship to the study treatment.

AEs will be recorded from the start of study drug treatment until 28 days following the last dose of treatment with the study drug.

If known, the event diagnosis should be recorded rather than listing individual signs or symptoms. AEs must be graded as being mild, moderate or severe and their approximate duration given. Definitions of severity are as follows:

Mild: an AE usually transient in nature and generally not interfering with normal activities;

Moderate: an AE that is sufficiently discomforting to interfere with normal activities;

Severe: an AE that is incapacitating and prevents normal activities.

Even if the Investigator feels there is no relationship to the study drug, all AEs MUST be recorded in the eCRF. The Investigator is requested to assess the relationship of any AEs to treatment using the following definitions:

Unrelated: those AEs which are clearly and incontrovertibly due to extraneous causes (concurrent drugs, environment etc.) and do not meet the criteria for drug relationship listed under Unlikely, Possible, Probable or Related.

Unlikely: an AE may be considered unlikely if it includes at least the first two features:

- It does not follow a reasonable temporal sequence from administration of the drug.

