### 10.1 Adverse Events

A treatment emergent AE is any reaction, side effect, or other untoward event, regardless of relationship to study drug, which occurs any time after the first dosing of study drug, until 28 days following the last dose of treatment with the study drug. During the study, clinically significant adverse changes in clinical status, ECGs, and physical examinations are considered AEs. Any patient complaints associated with such an abnormal finding will also be reported as an AE.

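### The follow-up visit list asks only for previously ongoing adverse events, in conflict with Section 12.1, Tables 2 and 4 and, for Part A, the SAP's 28-day window

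*Protocol*

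**What the plan says.** Protocol Section 10.6 places the visit four weeks after the final dose, in both parts of the study. Its list of assessments ends with the sole adverse-event task, "Record previously ongoing AEs/SAEs".

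Protocol Section 12.1 sets the general rule. On the period: "AEs will be recorded from the start of study drug treatment until 28 days following the last dose of treatment with the study drug". On how events are found: "Investigators will ask the patient at each visit if they have experienced any untoward occurrence since the last study visit". The same section insists that every adverse event be entered in the eCRF, whatever the investigator thinks of its cause.

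The schedules in Section 9.1.1 (Table 2 for Part A, Table 4 for Part B) have a column headed "Follow Up Visit 4 weeks after last dose"; Table 2 adds a window of ±5 days. Both mark the AEs/SAEs row in that column, and no footnote confines the mark to ongoing events.

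Protocol Section 9.4.4.1 explains that patients who stop study medication are asked back at four weeks so that safety information, lymphocyte recovery included, can be gathered and disease status assessed.

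SAP Section 10.1 treats an event as treatment-emergent if it occurs after first dosing and "until 28 days following the last dose of treatment with the study drug". SAP Section 2 limits that document to Part A and leaves the Part A extension and Part B to separate plans.

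**The concern.** An event that begins off drug, for example on day 10 after the last dose, falls inside the Section 12.1 collection period and outside the literal instruction in Section 10.6. In Part A the SAP would count it as treatment-emergent if it reached the database.

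The qualifier appears in no other visit list. The Early Termination list in Section 10.5, for instance, says simply "Record AEs/SAEs". A site comparing the two could reasonably take the narrower wording as intended.

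The period is a relevant one. Lymphocytes are recovering, and Section 9.1.2.5 names infections among the events of special interest. If some sites record new off-drug events and others do not, the post-treatment safety data are uneven. An event that nobody asks about may be impossible to recover later. A shortfall need not be equal across arms if discontinuation or off-drug event rates differ, though the documents give no figures from which to judge that.

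**Working it through.** The main check sets the texts side by side. Each row asks whether a new event starting within 28 days after the last dose should be recorded.

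| Source | Instruction for the off-drug period | New event recorded? |
|---|---|---|
| Protocol 10.6 | Record events already ongoing | Not asked for |
| Protocol 12.1 | All events to 28 days after last dose; ask about new ones at each visit | Yes |
| Protocol Table 2 (Part A) | AEs/SAEs marked at follow-up, unrestricted | Yes |
| Protocol Table 4 (Part B) | AEs/SAEs marked at follow-up, unrestricted | Yes |
| SAP 10.1 (Part A only) | Counted as treatment-emergent to day 28 | Counted if recorded |

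The Section 10.6 line is the one that does not fit.

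**Timing.** 4 weeks × 7 = 28 days, so the visit falls at the end of the collection period. With ±5 days in Part A it falls between day 28 − 5 = 23 and day 28 + 5 = 33. Tables 2 and 4 and Section 9.3 show no other routine visit after end of treatment or early termination.

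**Which text a site would use.** The opening of Section 11 describes the tables as an outline and points to Section 10 for further detail of procedures. A site wanting to know what the table's mark means would be sent to Section 10.6 and find the narrower task there. The tables therefore do not settle the conflict.

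**Share of observation time.** Share = 28 / (last dosing day + 28). The last dosing day is taken as the nominal final visit: Day 169 for Week 24 (Table 1) and Day 729 for Month 24 (Table 3).

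- Part A patient not entering the extension: 28 / (169 + 28) = 28 / 197 = 14.2%.
- Part B completer who stops drug at Month 24: 28 / (729 + 28) = 28 / 757 = 3.7%.
- Early discontinuation raises the share. As an illustration, a last dose on Day 85 (Week 12 in Part A) gives 28 / (85 + 28) = 28 / 113 = 24.8%.

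The plan gives no figure of its own to reproduce. The documents give no off-drug event rate, so these shares cannot be turned into numbers of events.

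A separate, smaller gap exists whatever the wording: a Part A visit held on day 23 leaves 28 − 23 = 5 days of the period without a scheduled contact.

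**The case against.** The strongest reply is that full collection at this visit is already required. Section 12.1 applies at each visit, and follow-up is a visit. The schedule tables, which many sites use as their checklist, mark adverse events there without restriction. Sections 12.6 and 12.7 require clinically significant laboratory changes and clinical findings to be recorded as adverse events, and the visit repeats hematology, chemistry, vital signs, ECG and the C-SSRS. Section 10.6 says to record ongoing events; it does not say to leave new ones out. All of this stands. It limits the consequence to possible inconsistency, but does not remove the contradiction.

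Four stronger readings are tempting, and the documents do not support them.

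- *This is the only contact in the period.* Section 12 has patients given telephone numbers for reporting adverse events, and Section 12.4 has existing events followed up. It is the only routinely scheduled visit, not the only route for a report.
- *Every other visit list uses the unrestricted wording.* The screening list has its own wording (SAEs from consent, AEs from first dose), and the Day 5 and Day 8 lists have no adverse-event line. What is true is that the restriction to ongoing events appears only in Section 10.6.
- *The SAP supports the point for both parts.* The SAP supplied covers the Part A placebo-controlled period only. It also defines what is counted and does not instruct sites. For Part B the conflict rests on Section 12.1 and Table 4.
- *SAEs are equally affected.* The line in Section 10.6 names SAEs, but the text available for Sections 12.2 and 12.3 is incomplete and may set a separate SAE reporting period. How far SAE capture is affected cannot be judged.

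**Conclusion.** The point holds as an internal inconsistency: Section 10.6 is wrong as written against the rest of the protocol. It is not a design choice, since Section 12.1 and both tables agree with one another, and for Part A the SAP agrees with them. It should be corrected, because the line governs safety collection at the last scheduled visit.

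The affected window is 28 days per patient who stops drug. The percentages assume that dosing ends on the nominal final visit day and that the patient does not continue into further treatment.

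A reader might infer that treatment-emergent rates are understated, or that 14% of Part A events are lost. Neither follows. The loss is zero wherever Section 12.1 or the tables are followed, and the documents do not show which text sites would use. The supported conclusion is that events beginning off drug may go unrecorded at some sites and that capture could vary between sites.

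**What to change.** Reconcile the sections by changing the adverse-event line in Section 10.6 to read *Record all new and ongoing AEs/SAEs*. That matches Section 12.1 and Tables 2 and 4, and agrees with the Part A SAP window.

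The cost is a one-line protocol correction. It adds no visit, procedure or patient burden, and needs no change to the SAP.
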